Regardless of indication, the success of colonoscopy is linked closely to the adequacy of preprocedure bowel cleansing. Quality of bowel preparation is based on ability to visualize the mucosa after retained stool and fluid have been suctioned away. The endoscopist should document the quality of the bowel preparation in each colonoscopy. [5] Unfortunately, up to 20%–25% of all colonoscopies are reported to have an inadequate bowel preparation. The reasons for this range from patient-related variables such as compliance with preparation instructions and a variety of medical conditions that make bowel cleansing more difficult to unit-specific factors (eg, extended wait times after scheduling of colonoscopy). Adverse consequences of ineffective bowel preparation include lower adenoma detection rates, longer procedural time, lower cecal intubation rates, increased electrocautery risk, and shorter intervals between examinations. [4]

Traditionally, patients are instructed to ingest only clear liquids the day before colonoscopy. Recent randomized trials report that a liberalized diet the day before colonoscopy is associated with better tolerance of the preparation and comparable or better bowel cleansing.

A less restrictive low residue diet may improve colonoscopy bowel preparation quality compared with a clear liquid diet, according to interim randomized controlled trial data presented at Digestive Disease Week in May, 2016. The mean Boston Bowel Preparation Score was 7.98 with the low residue diet vs. 7.54 with the clear liquid diet, which was not statistically significant; however, the low residue diet group had significantly more adequate bowel preparations (91.3% vs. 75.7%; P = .05). The study also showed the low residue diet improved patient satisfaction and tolerability, and could help to increase patient participation in colorectal cancer screening programs. [7]

However, there are nopublished local guidelines on the use of low residue diet for bowel preparation. There is also insufficient evidence to recommend specific dietary regimens for special populations such as the elderly , diabetes, chronic kidney disease, chronic liver disease patients.

Objectives

a. General:

To determine the efficacy of low residue diet for colonoscopy bowel preparation in the special populations (elderly, diabetes mellitus, chronic kidney disase, chronic liver disease) versus clear liquid diet using the Boston Bowel Preparation Scale (BBPS).

b. Specific

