improve patients' compliance and experience and may potentially improve their future participation in colorectal cancer prevention programs without compromising examination quality. We want to test the hypothesis that the use of a low residue diet the day prior to colonoscopy was not inferior to consuming clear fluids alone in patients undergoing colonoscopy. It is the researcher's hope that a low residue diet may help alleviate patient concerns with bowel preparation experience and potentially improve patient participation in colorectal cancer prevention programs without compromising examination quality. It is also the researchers hope to determine the efficacy of low residue diet in special populations (ie,diabetes mellitus, CKD,CLD and elderly)

Methodology

Study Area

The study will be conducted at the out-patient department (OPD), wards and endoscopy unit of Veterans Memorial Medical Center until target population is reached

Study Design

This study is a prospective single-blinded, randomized controlled non-inferiority trial. All eligible patients will be included in the study. Patients will be randomized using block randomization. There are no benefits or compensations that will be provided for the patients in this study.

Intervention

All eligible patients subjected for screening colonoscopy at the OPD and wards will be included in the study. Medical risk evaluation, if necessary, will be done even prior to enrollment. As in everyprocedure, the risks and complications of colonoscopy will be highly explained. Outmost care and safety during the procedure will be assured to the patients as this will all be done with the assistance of service consultants.

All the procedures will be done by the GI consultants and fellows in-training with the assistance of service consultant for the day (see Appendix A for the list of service consultants per day). The patients will be randomized into two groups: those following the low residue diet regimen, and those on the clear liquid diet regimen. Each patient will receive oral and written instructions regarding the diet and cathartics to be ingested prior to scheduled colonoscopy.

Those patients randomized to the clear liquid regimen will be asked to take only clear liquids the entire day before their procedure. The low residue diet regimen group will consume the prescribed low residue diet until 6 pm the day before the procedure or 12 hours prior to scheduled colonoscopy.

Bowel cleansing regimen

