[figure not shown]
All patients will be instructed to ingest the standard operating procedure (SOP) bowel cleansing agent of VMMC. Patients whose colonoscopy was scheduled at 8 AM will be instructed to take lactulose 60cc followed by 4-5 glasses of water at 1pm, 3pm and 5pm the day before the procedure. They will also be instructed to take bisacodyl 5mg/tab, 2 tablets followed by 4-5 glasses of water at 7pm. Those patients schedule after 8am will follow the same regimen. They will be instructed to take the lactulose and bisacodyl 15 hours and 12 hours respectively prior to colonoscopy.

[figure not shown]
Outcomes

[figure not shown]
The primary outcome is the efficacy or adequacy of bowel preparation. It will be measured by the Boston Bowel Preparation Scale (BBPS), which is a validated and reliable scale. Secondary outcomes such as patient's tolerability of the regimen will be assessed by inquiring on the occurrence of gastrointestinal symptoms related to the dietary regimen, i.e, nausea, vomiting, bloatedness, abdominal cramps/discomfort. Other outcomes such as cecal intubation rate, polyp detection rate and insertion/withdrawal time will also be measured.

The efficacy of bowel preparation will be assessed by three gastroenterology consultants blinded to the bowel preparation. An adequate bowel preparation will be given a BBPS score of ≥ 6 . The secondary outcomes will also be assessed on the day of the procedure. Before colonoscopy patients will be asked to complete a questionnaire to assess their tolerability, hunger score and satisfaction with the dietary regimen. A subgroup analysis to assess the efficacy of bowel preparation on special population will also be conducted.

Study Process

Study Population

Inclusion Criteria:

 All adults≥18 years of age scheduled for colonoscopy at VMMC and willing to sign informed consent were eligible for ourstudy

Exclusion Criteria:

- 1. Patients with bowel obstruction and/or bowel perforation
- 2. Presence of a colostomy and/or history of a partial colon resection
- 3. Active gastrointestinal bleeding
- 4. Pregnancy
- 5. Inflammatory bowel disease
- 6. Diverticulitis

Sample Size:

At 95% confidence interval and 80% power of test, the minimum required sample size is 75 patients per group. This is also based on the previous proportion of adequate bowel preparation of 91% among low residue diet while 76% for clear liquid diet.

Statistical Analysis:

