Baseline characteristics of the patients will be described as mean and standard deviation among continuous variables while percentage will be utilized for categorical data. In comparing the two groups, t-test will be used to compare means such as BBPSscore, while chi square test will be utilized for categorical variables such as proportion of adequate bowel preparation. All significant test will be done at 5 % level. A non inferiority margin of 0.05 was set. Medcalc statistical calculator will be utilized to carry out statistical computations.

Results

Patients Demographics

A total of 75 patientseach from low residue diet and clear liquid diet group were included in this study whose average age is 67.9 and 64.9 respectively (p=.0515). (Table 1). It also showed that around 82.7% of the patients in low residue are elderly, which is not significantly different from the resulting proportion of elderly patients in clear liquid diet group (72%). (Table 1) Moreover, both group is composed mostly of male (61% vs 75%, Low Residue vs Clear liquid), while proportion of occurrence of diabetes mellitus, chronic kidney disease and chronic liver disease is also not significantly different for the two groups.(Table 1). There were also no differences in terms of cecal intubation rate, withdrawal time, out patients and in patient's number.(Table 1).

Table 1. Patient Baseline Demographic Information

Profile	Low Residue Diet (n=75)	Clear Liquid Diet (n=75)	p value
Age (years), mean±sd	67.9 ± 9.5	64.9 ± 9.0	0.0515 ^{ns}
Elderly (>60), n,%	62 (82.7)	54 (72.0)	0.1200 ^{ns}
Sex, n,%			
Male	46 (61.3)	56 (74.7)	0.0811 ns

Female	29 (38.7)	19 (25.3)	
Comorbidities, n,%			
Diabetes Mellitus	32 (42.7)	29 (38.7)	0.6192 ns
Chronic Kidney Disease	11 (14.7)	6 (8.0)	0.1993 ns
Chronic Liver Disease	5 (6.7)	5 (6.7)	1.0000 ns
Others			
Cecal intubation rate	75 (100)	75(100)	1.0
Withrawal time	8.6±2.2	8.95±2.5	0.3642
In patients	44(58.7)	39(52)	0.4131
Out patients	31(41.3)	36(48)	

Adequacy of Bowel Preparation

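### The 75 per group reproduces only with an undeclared one-sided 5% level; with the two-sided 5% chi-square test that the protocol describes, 80% power needs 95 per group and 75 gives about 70%.

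*Protocol*

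**What the plan says.** The protocol's Sample Size section reads: "At 95% confidence interval and 80% power of test, the minimum required sample size is 75 patients per group". It bases this on the "previous proportion of adequate bowel preparation of 91% among low residue diet while 76% for clear liquid diet". These are rounded from an interim trial report cited in the introduction, where "the low residue diet group had significantly more adequate bowel preparations (91.3% vs. 75.7%; P = .05").

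Under Statistical Analysis, the "chi square test will be utilized for categorical variables such as proportion of adequate bowel preparation", and "All significant test will be done at 5 % level". A non-inferiority margin of 0.05 follows in the same paragraph, without a scale or an endpoint. Study Design adds: "This study is a prospective single-blinded, randomized controlled non-inferiority trial".

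None of these sections says whether the 5% is one-sided or two-sided. The Sample Size section names neither a test nor the margin.

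**The concern.** A 95% confidence level together with a chi-square test at 5% is ordinarily read as two-sided. For 91% against 76%, that reading needs clearly more than 75 per group for 80% power, so the sample-size statement and the analysis do not appear to describe the same test.

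This is the only power statement in the document, and it concerns the primary outcome. A reader who meets the non-significant adequacy comparison in the results (92.0% vs 90.7%) will take it that the chance of missing the assumed 15-point difference was 20%. Under the two-sided test it was about 30%.

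**Working it through.** **Inputs**
- Rates p1 = 0.91 and p2 = 0.76, difference d = 0.15 (Sample Size).
- Power 80%, so z = 0.8416 (Sample Size).
- Level 5% (95% confidence in Sample Size; 5% level in Statistical Analysis): z = 1.960 if two-sided, 1.645 if one-sided.
- Equal groups, with no allowance for dropout stated.

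**Formula** (pooled variance under the null, no continuity correction)

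n per group = [z_α·A + z_β·B]² / d², where
- A = √(2 × 0.835 × 0.165) = 0.5249
- B = √(0.91 × 0.09 + 0.76 × 0.24) = √0.2643 = 0.5141

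**The plan's own figure.** One-sided 5%: [1.645 × 0.5249 + 0.8416 × 0.5141]² / 0.0225 = 74.7, so **75 per group**. This is an exact match.

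**Two-sided 5%.** [1.960 × 0.5249 + 0.8416 × 0.5141]² / 0.0225 = 94.9, so **95 per group**. The choice of formula does not close the gap: two-sided, the unpooled version gives 93, the arcsine version 92 and the continuity-corrected version 108.

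**Power at 75 per group**, Φ[(d√75 − z_α·A) / B], with d√75 = 1.2990:
- Two-sided: (1.2990 − 1.0289) / 0.5141 = 0.526, so **70.0%**.
- One-sided: (1.2990 − 0.8634) / 0.5141 = 0.847, so **80.2%**.
- Exact enumeration of the uncorrected two-sided chi-square test: **71.8%**.

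**Unrounded source rates** (91.3% vs 75.7%, d = 0.156), two-sided: n = 87.7, so 88 per group; power at 75 is 73.5%.

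**Which sidedness does the document use?** The p-values for the group comparisons in Tables 2a and 3a can be recomputed. Two-sided Pearson values come very close. Multiplying the chi-square statistic by (N − 1)/N = 149/150 reproduces the printed figures to four decimals:

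| Comparison (LRD vs CLD, of 75) | Two-sided p, Pearson | Two-sided p, ×149/150 | Printed |
|---|---|---|---|
| Adequate preparation, 69 vs 68 | 0.7717 | 0.7724 | 0.7724 |
| Abdominal pain, 12 vs 26 | 0.0086 | 0.0088 | 0.0088 |
| Bloatedness, 20 vs 33 | 0.0264 | 0.0269 | 0.0269 |
| Willing to repeat, 70 vs 61 | 0.0271 | 0.0277 | 0.0277 |

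One-sided values in the observed direction would be half of these. The tests as carried out are two-sided.

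**Does the margin explain 75?** Assume that 0.05 means 5 percentage points on the adequacy proportion. With the same rates, n = (z_α + z_β)² × 0.2643 / (0.15 + 0.05)² gives 41 (one-sided 5%) or 52 (one-sided 2.5%). With equal true rates anywhere between 91% and 76%, n = (z_α + z_β)² × 2p(1 − p) / 0.05² gives 406 to 1,146 across the same two levels. None of these is 75.

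**The case against.** The best defence is that sidedness is never stated. One-sided at 5%, the standard formula gives exactly 75 and the power is 80.2%. The trial is declared as non-inferiority, where a one-sided test is a normal choice. The printed p-values show how the results were tested, not which level went into the planning calculation.

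Much of this stands. A reader might infer that 75 is an arithmetic slip, or that 75 cannot give 80% power at a 5% level. The documents support neither: the sum is right under one reading of an incomplete statement. The defect is an undeclared level that does not fit the rest of the text.

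The non-inferiority design does not rescue the figure, however. The calculation that yields 75 tests a zero difference against a 15-point difference and makes no use of the margin. A one-sided 5% test also corresponds to a 90% two-sided interval, whereas the Sample Size section cites 95% confidence.

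It is also fair to say that the shortfall shrinks with the unrounded source rates (88 needed, about 73% power) and that results on 75 per group are already reported. Restating the power therefore changes no estimate or p-value.

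**Conclusion.** The point holds as an inconsistency between the sample-size statement and the analysis described. The 75 per group rests on a one-sided 5% level that the protocol nowhere declares. With the two-sided 5% chi-square test, 95 per group are needed for 80% power. The planned 75 is 20 short (20/95 = 21%), and its power is about 70% to 72%, or about 73% to the same normal approximation with the unrounded rates.

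This rests on reading the 5% as two-sided. The protocol does not say so outright, but its 95% confidence, its chi-square test and its printed p-values all point that way.

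A reader might also infer that this trial should have enrolled 95 per group. The documents do not support that either: 95 is the size for detecting a 15-point difference, and the declared objective is non-inferiority. Neither 75 nor 95 speaks to that hypothesis.

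**What to change.** In the Sample Size section, replace the power sentence with wording such as: *75 patients per group give about 70% power to detect a difference between 91% and 76% adequate preparation with a two-sided 5% chi-square test (80% only if the test is one-sided at 5%). This is power to detect a difference. It does not use the 0.05 non-inferiority margin and is not the power for the non-inferiority hypothesis.*

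State the sidedness of the 5% level in Statistical Analysis as well, so that the two sections agree. If a one-sided level was intended, say so in both places and reconcile it with the 95% confidence and the two-sided p-values.

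The cost is a few sentences and a less favourable power figure. No patients, data or analyses change.

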The mean Boston Bowel Preparation Score was 7.00 ± 1.12 with the low residue diet(LRD) vs. 6.90 ± 1.12 with the clear liquid diet(CLD), which was not statistically significant. LRD bowel preparation quality was non inferior to CLD bowel preparation quality (LRD 7.0 vs. CLD 6.9) (Table 2). Bowel preparation was considered adequate if the BBPS score was equal or higher than 6. Both colon preparation regimens were adequate for colon cleansing (92% vs 90.7%). No significant differences were observed between the treatment groups(92% vs 90.7%, p=0.7724). Likewise, same conclusion can be derived from patients with Diabetes, Chronic Kidney Disease, chronic liver disease, and among elderly patients.(Table 2b-2e).

Table 2a. Boston Bowel Preparation Scale (BBPS) Scores

Outcome	Low Residue Diet (n=75) Clear Liquid Diet (n=75)		p value
BBPS Score, mean±sd	7.00 ± 1.12	6.90 ± 1.12	0.6095 ^{ns}
BBPS Score≥6, n, %	69 (92.0)	68 (90.7)	0.770.4ns
BBPS Score<6, n,%	6 (8.0)	7 (9.3)	0.7724 ^{ns}

Table 2b. Boston Bowel Preparation Scale (BBPS) Scores for Diabetes

Outcome	Low Residue Diet (n=32)	Clear Liquid Diet (n=29)	p value
BBPS Score, mean±sd	6.89 ± 1.17	7.01 ± 1.14	0.6722 ^{ns}
BBPS Score≥6, n, %	27 (84.4)	27 (93.1)	0.2894 ^{ns}

BBPS Score<6, n,%	5 (15.6)	2 (6.9)	
-------------------	----------	---------	--

Table 2c. Boston Bowel Preparation Scale (BBPS) Scores for CKD

Outcome	Low Residue Diet (n=11) Clear Liquid Diet (n=6)		p value
BBPS Score, mean±sd	6.79 ± 1.21	7.11 ± 1.19	0.6034 ^{ns}
BBPS Score≥6, n, %	10 (90.9)	6 (100.0)	1 00000
BBPS Score<6, n,%	1 (9.1)	0 (0.0)	1.000 ^{ns}

Table 2d. Boston Bowel Preparation Scale (BBPS) Scores for CLD

Outcome	Low Residue Diet (n=5)	Clear Liquid Diet (n=5)	p value
BBPS Score, mean±sd	7.33 ± 1.45	6.47 ± 1.50	0.3802 ^{ns}
BBPS Score≥6, n, %	4 (80.0)	4 (80.0)	1 00000
BPPS Score<6, n,%	1 (20.0)	1 (20.0)	1.000 ^{ns}

Table 2eBoston Bowel Preparation Scale (BBPS) Scores for Elderly (Age≥60)

Outcome	Low Residue Diet (n=62) Clear Liquid Diet (n=54)		p value
BBPS Score, mean±sd	7.06 ± 1.15	6.90 ± 1.09	0.4333 ^{ns}
BBPS Score≥6, n, %	57 (91.9)	49 (90.7)	0.010008
BBPS Score<6, n,%	5 (8.1)	5 (9.3)	0.8199 ^{ns}

Patient Tolerance and Satisfaction

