From a patient standpoint, bowel preparation remains the biggest deterrent to an elective colonoscopy examination. Bowel preparations are generally poorly tolerated, which results in an important impediment to colorectal cancer screening and surveillance. Tolerability, often measured in clinical trials with "willingness to retake the preparation" or with respect to taste of the purgative solution, involves other factors that may lead to negative patient assessment. These include various dietary modifications or restrictions and important adjustments in work or social schedule that may affect the pre-procedural quality of life and directly influence adherence.

Overall, patient's tolerability and satisfaction were better in the LRD group than the CLD group. The present study showed that the proportion of patients having abdominal pain/cramping/discomfort and bloatedness are significantly lower in LRD group compared to CLD group. In addition, the proportion of patients in the LRD group was less hungry before colonoscopy as compared to CLD group. Our study also showed a higher proportion of patients in the LRD group rated the procedure easy and fair compared to CLD group. These results were parallel to other studies.

However, in our subgroup analysis, no difference was found among diabetics, chronic kidney disease and chronic liver disease patients when the two groups were compared with regards to patient's tolerability and satisfaction.

The present study has some limitations. It is a single-center study with arelatively small sample size. In addition, another limitation of the study is the sample size included in the chronic kidney disease(total of 17) and chronic liver disease(10) were small compared to elderly population(116) and diabetics(61),hence we cannot totally assessed their impact on the adequacy of bowel preparation.

Conclusion

Patients on a low residue diet for bowel preparation achieved an adequate bowel preparation that is non-inferior to patients on a clear liquid diet. Furthermore, the study showed that patients tolerability and overall satisfaction were better on the low residue diet group. Patients

in the LRD group would be more willing to repeat the same bowel regimen as compared to CLD group. However, the study also showed no statistical significance on patient's tolerability and satisfaction among diabetics, chronic kidney disease and chronic liver disease patients.

REFERENCES:

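### Non-inferiority is concluded from non-significant tests of equality, and the document's own data do not meet the stated 0.05 margin

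*Protocol*

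**What the plan says.** Study Design in the Protocol states: "This study is a prospective single-blinded, randomized controlled non-inferiority trial". Statistical Analysis adds: "A non inferiority margin of 0.05 was set". It does not say whether 0.05 is a difference in proportions, in BBPS points or something else.

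The same section names the comparisons: "t-test will be used to compare means such as BBPSscore, while chi square test will be utilized for categorical variables", with the proportion adequately prepared given as an example of the latter. On the error rate it says only: "All significant test will be done at 5 % level", without sidedness. It specifies no confidence interval for the difference and no test against the margin.

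The Results (Adequacy of Bowel Preparation) describe the difference in mean BBPS as not significant (p = 0.6095 in Table 2a) and then state: "LRD bowel preparation quality was non inferior to CLD bowel preparation quality (LRD 7.0 vs. CLD 6.9". The proportions adequate, 92.0% and 90.7%, are compared with p = 0.7724, and the same conclusion is extended to the diabetes, kidney disease, liver disease and elderly subgroups. The Discussion repeats the claim. The Conclusion puts it on adequacy: LRD patients "achieved an adequate bowel preparation that is non-inferior to patients on a clear liquid diet".

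**The concern.** A t-test or chi-square test of equality asks whether the data rule out zero difference. Non-inferiority asks whether they rule out a deficit as large as the margin. A large p-value answers neither question, and a smaller trial produces one more easily. As written, the margin plays no part in the decision.

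The claim also moves between scales. The sample size and the Conclusion concern the proportion with BBPS of 6 or more, while the sentence in the Results rests on mean BBPS. A margin of 0.05 means something different on each.

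Non-inferiority is the trial's headline result. If the reported data do not support it, readers would take from the report an assurance about cleansing quality that was not obtained.

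**Working it through.** **Inputs.** Table 2a: adequate preparation 69/75 (LRD) and 68/75 (clear liquid); mean BBPS 7.00 (SD 1.12) and 6.90 (SD 1.12), 75 per group. Statistical Analysis: margin 0.05, 5% level. All differences are LRD minus clear liquid.

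**1. Which tests produced the reported p-values.** The uncorrected chi-square on 69/75 against 68/75 gives p = 0.772 (reported 0.7724). The t-test from the rounded means gives p = 0.585 (reported 0.6095; a mean difference nearer 0.095 would give 0.604, so rounding explains the gap). Both are ordinary tests of zero difference.

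**2. Proportion adequate.** Difference = 0.9200 - 0.9067 = +0.0133.

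SE = √(0.9200×0.0800/75 + 0.9067×0.0933/75) = √(0.000981 + 0.001128) = 0.0459.

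- Wald 95%: 0.0133 ± 1.960×0.0459 = -0.077 to +0.103.
- Wald 90% lower limit: 0.0133 - 1.645×0.0459 = -0.062.

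Newcombe's method combines the Wilson limits of the two arms (95%: 0.836 to 0.963 for LRD, 0.820 to 0.954 for clear liquid).

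| Method | 95% interval (points) | 90% lower limit (points) |
|---|---|---|
| Wald | -7.7 to +10.3 | -6.2 |
| Newcombe | -8.3 to +11.0 | -6.6 |
| Score | -8.5 to +11.4 | -6.7 |

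Every lower limit is below -5 points. The one-sided p-value against -5 points is 0.084 (Wald) to 0.093 (score), so the claim fails at one-sided 2.5% and at 5%.

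**3. Mean BBPS, margin read as 0.05 points.** SE = 1.12×√(2/75) = 0.183. With t(148): 95% interval 0.10 ± 1.976×0.183 = -0.26 to +0.46; 90% lower limit 0.10 - 1.655×0.183 = -0.20. Both lower limits are below -0.05; one-sided p = 0.21.

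**4. Margin read as 5% of the mean score.** 0.05×6.90 = 0.345 points. The 95% lower limit of -0.26 would clear this. Nothing in the protocol states this reading.

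**5. Subgroups (proportion adequate).**

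| Subgroup | LRD | Clear liquid | Difference (points) | Newcombe 95% lower limit |
|---|---|---|---|---|
| Diabetes | 27/32 | 27/29 | -8.7 | -25.6 |
| Kidney disease | 10/11 | 6/6 | -9.1 | -37.7 |
| Liver disease | 4/5 | 4/5 | 0.0 | -45.5 |
| Elderly | 57/62 | 49/54 | +1.2 | -9.6 |

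In diabetes and kidney disease the point estimate itself lies beyond -5.

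**6. How often non-significance would lead to a false claim.** This is exact binomial enumeration with 75 per arm and an assumed 91% on clear liquid. If LRD is truly 86%, the chi-square is non-significant with probability 0.84. If LRD is truly 81%, the probability is 0.57. A valid test would allow 2.5% (or 5%) at the margin.

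**7. What 75 per group can show.** With both true rates at 91%, SE = √(2×0.91×0.09/75) = 0.0467. Power to meet a 5-point margin is Φ(0.05/0.0467 - 1.960) = 0.19 at one-sided 2.5%, or Φ(0.05/0.0467 - 1.645) = 0.28 at one-sided 5%. For 80% power, n per group = (1.960 + 0.842)²×2×0.91×0.09/0.05² = 515, or 406 with 1.645.

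**The case against.** The protocol never writes down a rule that non-significance means non-inferiority. The sentence in the Results also cites means that favour LRD. If the implicit rule were non-significant and LRD not numerically lower, the false-claim probabilities in step 6 would fall to about 20% (true deficit 5 points) and 5% (true deficit 10 points). That is fair: 84% and 57% are the upper end of a range. But 20% is still far above 2.5%. Extending the same conclusion to diabetes, where LRD was lower (84.4% against 93.1%), fits the plain non-significance rule better.

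Because the margin has no scale, it cannot be said to be missed on every conceivable reading; a margin of 5% of the mean score would be met. That is correct, but no text supports that reading, and the sample size and the Conclusion are both on proportions.

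A separate analysis plan might specify the right test. It could not repair this document, which names its tests, reports their results and draws the conclusion.

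Lastly, the point estimates slightly favour LRD and nothing here shows it to be inferior overall. That stands, and it limits the correction to not demonstrated.

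**Conclusion.** The concern holds. Tests of equality stand in for a non-inferiority analysis, and the margin is never used. Read as 5 percentage points of adequacy or as 0.05 BBPS points, it is not met at one-sided 2.5% or 5%. The 95% lower limits are -7.7 to -8.5 points against -5, and -0.26 against -0.05. The proportion result holds for all three interval methods in the working.

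This rests on the counts and rounded means in Table 2a and on 0.05 being an absolute difference. The false-claim probabilities further assume 91% adequacy on clear liquid and depend on which implicit rule was applied: about 20% to 84% at a true 5-point deficit. The proper reading is inconclusive, which is unsurprising given 19% to 28% power under equal true rates. The headline conclusion must be corrected.

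**What to change.** In Statistical Analysis, state the scale of the margin and the one-sided error rate, and replace the primary test with wording such as: LRD is non-inferior if the lower limit of the two-sided 95% confidence interval (Newcombe or Miettinen-Nurminen) for the difference in the proportion with BBPS of 6 or more, LRD minus clear liquid, lies above -5 percentage points. Make mean BBPS secondary, and keep the t-test and chi-square for secondary comparisons.

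In the Results, Discussion and Conclusion, report a difference of +1.3 points, 95% interval about -8 to +11, with non-inferiority at the 5-point margin not demonstrated and inferiority not shown. Withdraw the extension to the subgroups. Since the results are already in the document, say what trial records show was fixed beforehand and label any later choice of scale, level or method as post hoc.

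The cost is one interval from data in hand, some rewording and a less favourable conclusion. Rewording cannot supply the missing precision: 80% power at this margin with equal true rates of 91% would need about 406 to 515 per group.
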